#### 3.1.2 Safety Parameters

The safety of acalabrutinib in combination with R-ICE will be characterized by the type, frequency, severity, timing of onset, duration, and relationship to study drug of any treatment-emergent AEs or abnormalities of laboratory tests; SAEs; DLTs, or AEs leading to discontinuation of study treatment or death.

The descriptions and grading scales found in the revised NCI Common Terminology Criteria for Adverse Events (CTCAE) version 5.0 will be utilized for adverse event reporting. (see [Section 6](#)).

#### 3.1.3 Pharmacodynamic, Pharmacokinetic and Biomarker Parameters

Exploratory correlative studies of tumor tissue, when available, may include characterization of tumor subtypes by NGS, including comparing pre- and post- study treatment biopsies in patients without a clinical response and/or progression of disease. Baseline and end of treatment (EOT) PET scan will be assessed for response by MTV as a correlative biomarker.

### 3.2 RATIONALE FOR STUDY DESIGN AND DOSING REGIMEN

As described in Section 1.4, acalabrutinib is currently being evaluated in a Phase 1/2 study in subjects with CLL, Richter's syndrome, or prolymphocytic leukemia (ACE-CL-001). In this study, subjects have received oral dosages of 100 to 400 mg QD and 100 to 200 mg BID of acalabrutinib. All tested dose levels have been well tolerated. No DLT has occurred at any dose level and the MTD was not reached. PD results from this study also show 100 and 200 mg BID have the highest Btk occupancy at 24 hours of all the regimens evaluated. Robust clinical responses have been observed (Investigator Brochure 9.0 section 5.2.3.1).

The dosing of R-ICE has been extensively studied including in phase I with the BTK inhibitor ibrutinib.

### 3.3 SELECTION OF STUDY POPULATION

#### 3.3.1 Inclusion Criteria

Eligible subjects will be considered for inclusion in this study if they meet **all** of the following criteria:

1. Men and women  $\geq$  18 years of age.
2. Patients must have histologic confirmation of relapsed or refractory lymphoma.
3. Baseline FDG-PET scans must demonstrate positive lesions compatible with CT defined anatomical tumor sites.
  - a) CT scan showing at least:
    - i) 2 or more clearly demarcated lesions/nodes with a long axis  $>1.5\text{cm}$  and short axis  $\geq 1.0\text{cm}$ , or
    - ii) 1 clearly demarcated lesion/node with a long axis  $>2.0\text{cm}$  and short axis  $\geq 1.0\text{cm}$ .
4. Patient must have been previously treated for B cell non-Hodgkin lymphoma with any of the allowable below:
  - a) First-line treatment with rituximab and an anthracycline-based chemotherapy.
  - b) Monotherapy rituximab, dosed prior to first-line rituximab combined with anthracycline containing chemotherapy, or as maintenance therapy.
  - c) Radiotherapy as part of the first-line treatment plan including anthracycline and rituximab.
5. Eastern Cooperative Oncology Group (ECOG) performance status of 0 to 2 (See Appendix 2)
6. Life expectancy of greater than 6 weeks.
7. Patients must have normal organ and marrow function as defined below,
  - a) absolute neutrophil count  $\geq 1000/\text{mcL}$  (unless due to lymphoma involvement of the bone marrow)
  - b) platelets  $\geq 75,000/\text{mcL}$  (unless due to lymphoma involvement of the bone marrow)
  - c) total bilirubin  $<1.5 \times$  within normal institutional limits (unless due to lymphoma involvement of liver or a known history of Gilbert's disease)
  - d) AST(SGOT)/ALT(SGPT)  $\leq 2.5 \times$  institutional upper limit of normal (unless due to lymphoma involvement of liver)
  - e) creatinine within normal institutional limits, or
  - f) creatinine clearance  $\geq 40 \text{ mL/min}/1.73 \text{ m}^2$  for patients with creatinine levels above institutional normal. (unless due to lymphoma)
8. Major surgical procedure within 28 days of first dose of study drug. If a subject had major surgery, they must have recovered adequately from any toxicity and/or complications from the intervention before the first dose of study drug.
9. Women who are sexually active and can bear children must agree to use highly effective forms of contraception during the study and for 90 days after the last dose of acalabrutinib + R-ICE.
10. Men who are sexually active and can beget children must agree to use highly effective forms of contraception during the study and for 90 days after the last dose of acalabrutinib + R-ICE.
11. Men must agree to refrain from sperm donation during the study and for 90 days after the last dose of study drug.
12. Willing and able to participate in all required evaluations and procedures in this study protocol including swallowing capsules without difficulty.
13. Ability to understand the purpose and risks of the study and provide signed and dated informed consent and authorization to use protected health information (in accordance with national and local subject privacy regulations).

#### 3.3.2 Exclusion Criteria

Subjects will be ineligible for this study if they meet **any** of the following criteria:

1. Germinal-center cell-of-origin DLBCL

2. Patients who have had chemotherapy or radiotherapy < 21 days prior to first administration of study treatment or those who have not recovered from adverse events due to agents administered more than 4 weeks earlier.
3. Patients who are receiving any other investigational agents.
4. Patients with known central nervous system involvement of lymphoma.
5. History of allergic reactions attributed to compounds of similar chemical or biologic composition to acalabrutinib or R-ICE with the exception of first-infusion reaction to rituximab.
6. Uncontrolled intercurrent illness including, but not limited to, ongoing or active infection, symptomatic congestive heart failure, unstable angina pectoris, cardiac arrhythmia, or psychiatric illness/social situations that would limit compliance with study requirements. Recent infections requiring systemic treatment need to have completed therapy > 7 days before the first dose of study drug.
7. Pregnant women are excluded from this study because an acalabrutinib R-ICE is a chemotherapy program with the potential for teratogenic or abortifacient effects. Because there is an unknown but potential risk for adverse events in nursing infants secondary to treatment of the mother with acalabrutinib R-ICE, breastfeeding should be discontinued if the mother is treated with acalabrutinib R-ICE.
8. HIV-positive patients on combination antiretroviral therapy are eligible, unless the patient's CD4 count is below the institutional lower limit of normal, or the patient is taking prohibited CYP3A4/5 strong inhibitors or inducers.
9. Patients may not have received any anti-cancer therapy for their primary rel/ref DLBCL with the exception of palliative RT.
10. Uncontrolled Autoimmune Hemolytic Anemia or ITP resulting in (or as evidenced by) declining platelet or Hgb levels within the 4 weeks prior to first dose of study drug.
11. Presence of transfusion-dependent thrombocytopenia.
12. Prior exposure to a BTK inhibitor.
13. History of prior malignancy, with the exception of the following:
  - a) Malignancy treated with curative intent felt to be at low risk for recurrence by treating physician
  - b) Adequately treated non-melanomatous skin cancer or lentigo maligna melanoma without current evidence of disease
  - c) Adequately treated cervical carcinoma in situ without current evidence of disease.
14. Currently active clinically significant cardiovascular disease such as uncontrolled arrhythmia, congestive heart failure, or Class 3 or 4 congestive heart failure as defined by the New York Heart Association Functional Classification, or history of myocardial infarction, unstable angina, or acute coronary syndrome within 6 months prior to first dose with study drug.
15. Unable to swallow capsules, or disease significantly affecting gastrointestinal function or, resection of the stomach or small bowel, or symptomatic inflammatory bowel disease or ulcerative colitis, or partial or complete bowel obstruction.
16. Serologic status reflecting active hepatitis B or C infection. Patients that are positive for hepatitis B core antibody, hepatitis B surface antigen (HBsAg), or hepatitis C antibody will need a negative polymerase chain reaction (PCR) prior to enrollment. (PCR positive patients will be excluded.) Hepatitis C antibody positive patients are eligible if PCR is negative. Hepatitis B core antibody (+) patients without evidence of HBsAg or Hep B PCR (+) are eligible with appropriate Hepatitis B reactivation prophylaxis.
17. History of stroke or intracranial hemorrhage within 6 months prior to enrollment.
18. Current life-threatening illness, medical condition, or organ system dysfunction which, in the Investigator's opinion, could compromise the patient's safety, or put the study at risk.
19. Received anticoagulation therapy with Coumadin or equivalent vitamin K antagonists within the last 28 days.
20. Vaccinated with live, attenuated vaccines with 4 weeks of first does of study drug.

21. Unresolved toxicities from prior anti-cancer therapy, defined as having not resolved to Common Terminology Criteria for Adverse Event (CTCAE, version 5), grade ≤1, or to the levels dictated in the inclusion/exclusion criteria with the exception of alopecia.
22. Known bleeding disorders (e.g., von Willebrand's disease) or hemophilia.
23. Unwilling or unable to participate in all required study evaluations and procedures.
24. Currently active, clinically significant hepatic impairment ( $\geq$  moderate hepatic impairment according to the NCI/Child Pugh classification).
25. Breastfeeding or pregnant.
26. Concurrent participation in another therapeutic clinical trial.
27. Patients who require proton pump inhibitors at baseline (prior to first dose of study drug) or strong CYP3A4 inhibitor or inducer and are not able to switch to another medication

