	

8. HIV-positive patients on combination antiretroviral therapy are eligible, unless the patient's CD4 count is below the institutional lower limit of normal, or the patient is taking prohibited CYP3A4/5 strong inhibitors or inducers.

9. Patients may not have received any anti-cancer therapy for their primary rel/ref DLBCL with the exception of palliative RT.

10. Uncontrolled Autoimmune Hemolytic Anemia or ITP resulting in (or as evidenced by) declining platelet or Hgb levels within the 4 weeks prior to first dose of study drug.

11. Presence of transfusion-dependent thrombocytopenia.

12. Prior exposure to a BTK inhibitor.

13. History of prior malignancy, with the exception of the following:

a) Malignancy treated with curative intent felt to be at low risk for recurrence by treating physician

b) Adequately treated non-melanomatous skin cancer or lentigo maligna melanoma without current evidence of disease

c) Adequately treated cervical carcinoma in situ without current evidence of disease.

14. Currently active clinically significant cardiovascular disease such as uncontrolled arrhythmia, congestive heart failure, or Class 3 or 4 congestive heart failure as defined by the New York Heart Association Functional Classification, or history of myocardial infarction, unstable angina, or acute coronary syndrome within 6 months prior to first dose with study drug.

15. Unable to swallow capsules, or disease significantly affecting gastrointestinal function or, resection of the stomach or small bowel, malabsorption syndrome or symptomatic inflammatory bowel disease or ulcerative colitis, or partial or complete bowel obstruction.

16. Serologic status reflecting active hepatitis B or C infection. Patients that are positive for hepatitis B core antibody, hepatitis B surface antigen (HBsAg), or hepatitis C antibody will need a negative polymerase chain reaction (PCR) prior to enrollment. (PCR positive patients will be excluded.) Hepatitis C antibody positive patients are eligible if PCR is negative. Hepatitis B core antibody (+) patients without evidence of HBsAg or Hep B PCR (+) are eligible with appropriate Hepatitis B reactivation prophylaxis.

17. History of stroke or intracranial hemorrhage within 6 months prior to enrollment.

18. Current life-threatening illness, medical condition, or organ system dysfunction which, in the Investigator's opinion, could compromise the patient's safety, or put the study at risk.

19. Received anticoagulation therapy with Coumadin or equivalent vitamin K antagonists within the last 28 days.

20. Vaccinated with live, attenuated vaccines within 4 weeks of first dose of study drug.

21. Unresolved toxicities from prior anti-cancer therapy, defined as having not resolved to Common Terminology Criteria for Adverse Event (CTCAE, version 4), grade <math>\leq 1</math>, or to the levels dictated in the inclusion/exclusion criteria with the exception of alopecia.

22. Known bleeding disorders (e.g., von Willebrand's disease), elevated PT/INR/aPTT <math>> 2x</math> normal, active bleeding or hemophilia.

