#### **4.1.5 Confirmation of Eligibility**

Subject eligibility for enrollment will be assessed per [Section 3.3](#). All screening procedures, unless otherwise indicated, should be completed within 28 days of the first dose of study drug.

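### Exclusion 22 differs between two current lists: the synopsis bars PT/INR/aPTT above 2x normal and active bleeding, while the operative list in Section 3.3.2 sets no coagulation limit and does not name active bleeding

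*Combined protocol and SAP*

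**What the plan says.** Section 3.3.2, item 22, excludes "Known bleeding disorders (e.g., von Willebrand's disease) or hemophilia". The synopsis list carries the same item number with a longer text. It begins "Known bleeding disorders (e.g., von Willebrand's disease), elevated PT/INR/aPTT", sets the limit for those tests at more than 2x normal, and ends "active bleeding or hemophilia".

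Section 4.1.5 states which list sites use: "Subject eligibility for enrollment will be assessed per" Section 3.3. Section 4.1.14 defines the coagulation panel as PT, aPTT and INR, and Appendix 1 schedules it at screening. Neither place attaches an eligibility limit to the result.

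Section 1.4.2.1 reports that serious hemorrhage, some of it fatal, has occurred in clinical studies of acalabrutinib.

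**The concern.** Two eligibility rules with the same number, both in force, do not say the same thing, and the one that sites are told to apply is the less restrictive. The difference concerns bleeding, a stated and sometimes fatal risk of the study drug. It is added to a chemotherapy backbone for which Section 3.8 lists thrombocytopenia among the main toxicities, and Section 3.8 also says the combination has not been studied in phase I.

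The direct stake is patient safety and consistent enrollment: three centers could treat the same screening result differently, depending on which list their staff use. There is also a possible effect on the safety lead-in. Under Section 3.8, a hemorrhagic event of grade 2 or higher that needs medical intervention is a dose-limiting toxicity, and one such toxicity in the first 3 patients triggers the lower acalabrutinib dose. A patient who enters with an unrecognized coagulation problem could therefore influence the study dose. The documents give no probability for that.

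**Working it through.** No arithmetic applies. The check compares the texts and then searches for a limit elsewhere.

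**Step 1. Exclusion 22, element by element.**

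| Element | Synopsis item 22 | Section 3.3.2 item 22 |
|---|---|---|
| Known bleeding disorders | yes | yes |
| PT/INR/aPTT above 2x normal | yes | no |
| Active bleeding | yes | no |
| Hemophilia | yes | yes |

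The Section 3.3.2 sentence is complete and grammatical, so nothing suggests that text was lost from it. The protocol revision history records no change to item 22.

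**Step 2. Which list governs.** Section 4.1.5 points to Section 3.3, and Section 3.3.2 makes a subject ineligible on any one listed criterion. The shorter item is the operative one.

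**Step 3. Is there a coagulation limit elsewhere in the body?** Inclusion 7 sets limits for neutrophils, platelets, bilirubin, transaminases and renal function, but none for PT, INR or aPTT. Exclusion 19 is "Received anticoagulation therapy with Coumadin or equivalent vitamin K antagonists within the last 28 days", which concerns a drug, not a laboratory value. Exclusion 24 uses a hepatic impairment class, not a stand-alone coagulation limit. Section 4.1.14 and Appendix 1 with its footnotes give none. The only limit in the document is the one in the synopsis.

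**Step 4. Is active bleeding covered elsewhere in the body?** No criterion names it, but several can reach it:

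- Exclusion 6, "Uncontrolled intercurrent illness including, but not limited to, ongoing or active infection" and other examples, is an open list. Uncontrolled active bleeding can fall under it as written.
- Exclusion 18 covers conditions that, "in the Investigator's opinion, could compromise the patient's safety".
- Exclusion 17, "History of stroke or intracranial hemorrhage within 6 months prior to enrollment", covers bleeding at that one site.
- Exclusions 2 and 21 cover unresolved toxicity from earlier therapy.
- Inclusion 8 requires adequate recovery from the complications of major surgery.

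This list shows partial cover and is not meant to be exhaustive.

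**Step 5. A worked case.** Take a patient with an aPTT of 2.5x normal, no known bleeding disorder and no vitamin K antagonist in the last 28 days. The value 2.5 is chosen for illustration.

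- Synopsis item 22: 2.5 > 2, so the patient is excluded.
- Section 3.3.2 item 22: no known bleeding disorder and no hemophilia, so it does not apply.
- Section 3.3.2 item 19: does not apply.
- No other body criterion refers to the aPTT result. Exclusion would need some other finding, or the investigator's opinion under item 18.

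**The case against.** The strongest reply is that the body is the controlling text and the synopsis is a stale summary. Section 4.1.5 gives sites a single list. The synopsis does lag elsewhere: its exclusion 21 cites CTCAE version 4 where Section 3.3.2 cites version 5, and it still describes MedDRA coding where Section 3.1.2 relies on CTCAE version 5.0. On this view the shorter item 22 is the intended one, and the clinical cover listed above is enough. It can be added that item 22 in the body is open-ended, so a marked coagulation abnormality might be classed as a known bleeding disorder.

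Part of this stands. A reader might infer that the body lets in actively bleeding patients without restraint. The documents do not support that, since exclusion 6 alone can bar uncontrolled bleeding and carries no wording that leaves it to the investigator's opinion. A reader might equally infer that the limit was dropped from the body by mistake, or removed from it on purpose. Neither is shown. The drift between the lists runs both ways: the body's item 6 adds heart failure and unstable angina, while the synopsis's item 15 adds malabsorption.

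The reply does not reach the laboratory limit. An isolated prolonged aPTT is not clearly a known bleeding disorder, and no other body criterion addresses it. Even if the synopsis is the stale text, one of the two lists has to be corrected.

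**Conclusion.** The conflict is real and should be resolved. The main gap is the missing PT/INR/aPTT limit: the body collects the test at screening and gives no rule for using the result. The gap for active bleeding is secondary, because other criteria cover part of it.

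The size in patients cannot be given, since the documents contain no rate of abnormal coagulation results or of bleeding at screening. It would be wrong to infer that the efficacy design is affected: the Simon design's sample size, decision boundaries and stated error rates do not depend on this item.

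The conclusion rests on two readings. Both lists are current text, not a record of superseded wording. Section 4.1.5 means what it says in directing sites to Section 3.3. Which wording the sponsor intends remains open.

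**What to change.** Use one version of exclusion 22 in both places. Given the hemorrhage risk in Section 1.4.2.1, the default is to bring the synopsis wording into Section 3.3.2, item 22: "Known bleeding disorders (e.g., von Willebrand's disease), elevated PT/INR/aPTT" > 2x the institutional upper limit of normal, "active bleeding or hemophilia". Reading normal as the institutional upper limit follows the convention that inclusion 7d already uses for AST and ALT. This default is a safety preference, and the sponsor should confirm it. If the shorter text is intended, delete the two additional elements from the synopsis.

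An optional addition is a statement on whether prolongation caused by a permitted anticoagulant counts. Section 3.9.2 prohibits only vitamin K antagonists, and Section 3.9.2.4 asks for monitoring of patients on antiplatelet or anticoagulant therapy.

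The cost is one line of eligibility text. No new procedure is needed, because the panel is already drawn at screening. The downside is that some patients may become ineligible, possibly including some on permitted anticoagulants other than vitamin K antagonists.

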### **3.3.3 Recruitment**

Investigators and designated personnel from the research study team at University of Miami Sylvester Comprehensive Cancer Center (SCCC) and if applicable other sites (for multi-center studies) will identify, recruit, enroll and treat eligible patients for the study. This study will access electronic medical record or other protected health information without obtaining a signed HIPAA authorization from the subject to identify potential subjects for recruitment and to obtain study data. At the University of Miami SCCC, subjects will be recruited via clinical practice offices. Additional study sites will recruit subjects as per institutional guidelines.

## **3.4 STUDY INTERVENTION DISCONTINUATION AND PARTICIPANT DISCONTINUATION/WITHDRAWAL**

### **3.4.1 Discontinuation of Study Intervention**

Discontinuation from protocol treatment does not mean discontinuation from the study, and remaining study procedures should be completed as indicated by the protocol. If a clinically significant finding is identified (including, but not limited to changes from baseline) after enrollment, the Investigator or qualified designee will determine if any change in participant management is needed. Any new clinically relevant finding will be reported as an adverse event (AE).

The data to be collected at the time of study intervention discontinuation will include the data collected during the safety evaluation visit and follow-up information.

### **3.4.2 Participant Discontinuation/Withdrawal from the Study**

Participants are free to withdraw from participation in the study at any time upon request. An Investigator may discontinue or withdraw a participant from the study for the following reasons:

- Pregnancy
- Significant study intervention non-compliance
- If any clinical adverse event (AE), laboratory abnormality, or other medical condition or situation occurs such that continued participation in the study would not be in the best interest of the participant
- Disease progression which requires discontinuation of the study intervention
- If the participant meets an exclusion criterion (either newly developed or not previously recognized) that precludes further study participation
- Participant unable to receive investigational treatment for 21 days/weeks.

The reason for participant discontinuation or withdrawal from the study will be recorded on the Case Report Form (CRF).

